Appendix 3: Attitudes Towards PrEP

Attitudes toward future PrEP usage

What effect do you think being screened today in the Emergency Department will have on your future PrEP use?

Less likely to start PrEP 0	1	2	No effect on future PrEP use 3	4	5	More Likely to start PrEP 6	Prefer not to answer
--------------------------------	---	---	-----------------------------------	---	---	--------------------------------	----------------------

Would you be interested in starting PrEP today if we were able to give you the medications in the Emergency Department

Would not be interested in starting today 0	1	2	3	4	5	Would start medication today if available 6	Prefer not to answer
--	---	---	---	---	---	--	----------------------

What do you think about an oral HIV prevention method?

What do you think you might like about an oral method? *Check all that apply.*

- Nothing
- May protect against HIV
- Easier to use than other methods (e.g., condoms)
- Can be used discreetly, without a partner's knowledge
- Does not interrupt sex
- Easily reversible
- Other, specify: _____
- Prefer not to answer

What concerns do you have about an oral HIV prevention method?

- None
- May not protect against HIV
- May cause harmful side effects
- Requires taking a daily pill
- Cannot be used discreetly, without a partner's knowledge
- Cost may be unaffordable
- Other, specify: _____
- Prefer not to answer

Appendix 4: CSBQ

CDC Sexual Behavior Questions (CSBQ)

FIRST TIER QUESTIONS

The next questions are about your sexual behavior. By sex we mean oral, vaginal, or anal sex, but NOT masturbation. When we talk about condoms, we mean both male as well as female condoms.

1. During the past 12 months, have you had sex?

Yes [1] No [2] SKIP to END Refused [9] SKIP to END
[NHSDA]

2. During the past 12 months, with how many people have you had sex?

Number [...] Don't know / Not sure [enter 777] Refused [enter 999]
[BRFSS; NHSDA]

3. During the past 12 months, have you had sex with only males, only females, or with both males and females?

Only males [1] Only females [2] Both males and females [3] Refused [9]
[NHSDA]

w, thinking back about the last time you had sex, did you or your partner use a condom? Yes [1] No [2]
ed [9]

[NHSDA; BRFSS; YRBS]

5. I'm going to read you a list. When I'm done, please tell me if any of the situations apply to you. You don't need to tell me which one.

You have used intravenous drugs in the past year You have been treated for a sexually transmitted disease or venereal disease in the past year You tested positive for having HIV, the virus that causes AIDS You have had more than one sex partner in the past year During the past 12 months you have given or received money or drugs in exchange for sex

Do any of these situations apply to you?

Yes [1] No [2] Refused [9]

[BRFSS, adapted]

END OF FIRST TIER QUESTIONS

ALTERNATE FIRST TIER QUESTIONS

The next questions are about your sexual behavior. By sex we mean oral, vaginal, or anal sex, but NOT masturbation. When we talk about condoms, we mean both male as well as female condoms.

1. During the past 12 months, have you had sex?

Yes [1] No [2] SKIP to END Refused [9] SKIP to END

[NHSDA]

2. During the past 12 months, with how many people have you had sex?

Number [...] Don't know / Not sure [enter 777] Refused [enter 999]

[BRFSS; NHSDA]

3. During the past 12 months, have you had sex with only males, only females, or with both males and females?

Only males [1] Only females [2] Both males and females [3] Refused [9]

[NHSDA]

4. I'm going to read you a list. When I'm done, please tell me if any of the situations apply to you. You don't need to tell me which one.

You have used intravenous drugs in the past year You have been treated for a sexually transmitted disease or venereal disease in the past year You tested positive for having HIV, the virus that causes AIDS You have had more than one sex partner in the past year During the past 12 months you have given or received money or drugs in exchange for sex

Do any of these situations apply to you?

Yes [1] No [2] Refused [9]

[BRFSS, adapted]

The next questions are about sex with a main partner.

5. In the past 12 months have you had sex with someone who you consider to be your main sex partner, that is a person who you feel committed to above anyone else?

Yes [1] No [2] SKIP to QUESTION 8 Refused [9] SKIP to QUESTION 8

[DA- Adapted]

If you had more than one main partner during the past 12 months, we would like you to think of the main partner you had last sex with.

6. Is this person a man or a woman?

Man [1] Woman [2] Refused [9]

7. Now, thinking back about the last time you had sex, did you or your partner use a condom?

Yes [1] No [2] Refused [9]

[NHSDA; BRFSS; YRBS]

8. In the past 12 months, have you had sex with someone who is not your main partner or whom you did not consider to be your main partner at the time?

Yes [1] No [2] SKIP to END Refused [9] SKIP to END

For the next series of questions, think back to the last time you had sex with someone who is/was not your main partner.

9. Is this person a man or a woman?

Man [1] Woman [2] Refused [9]

10. Now, thinking back about the last time you had sex, did you or your partner use a condom?

Yes [1] No [2] Refused [9]

[NHSDA; BRFSS; YRBS]

END OF ALTERNATE FIRST TIER QUESTIONS

SECOND TIER QUESTIONS

The next questions are about your sexual behavior. By sex we mean oral, vaginal, or anal sex, but NOT masturbation. When we talk about condoms, we mean both male as well as female condoms.

1. During the past 12 months, have you had sex?

Yes [1] No [2] SKIP to END Refused [9] SKIP to END

[NHSDA]

2. During the past 12 months, with how many people have you had sex?

Number [...] Don't know / Not sure [enter 777] Refused [enter 999]

[BRFSS; NHSDA]

3. During the past 12 months, have you had sex with only males, only females, or with both males and females?

Only males [1] Only females [2] Both males and females [3] Refused [9]

[NHSDA]

4. During the past 12 months, has a doctor or other health professional told you that you had a sexually transmitted disease, or STD, for example, herpes, gonorrhea, chlamydia, genital warts?

Yes [1] No [2] Don't know / Not sure [7] Refused [9]

[HITS]

5. Have you ever been told by a doctor or other health professional that you were infected with HIV or that you have AIDS?

Yes [1] No [2] Don't know / Not sure [7] Refused [9] [RBA, adapted]

6. During the past 12 months, have you given drugs in exchange for sex or received drugs in exchange for sex ?

x we mean vaginal, oral, or anal sex.

[1] No [2] Refused [9]

[DA]

7. During the past 12 months, have you given money in exchange for sex or received money in exchange for sex? By sex we mean vaginal, oral, or anal sex.

Yes [1] No [2] Refused [9]

[NHSDA; Some surveys have combined questions 6 and 7, for example: In the past 12 months, have you given or taken money or drugs in exchange for sex? (NHIS-Supplement)]

If respondent is female: SKIP to SECOND TIER QUESTION 26

[MALE RESPONDENTS ONLY]

The next questions are about sex with a main partner.

8. In the past 12 months have you had sex with someone who you consider to be your main sex partner, that is a partner who you feel committed to above anyone else?

Yes [1] No [2] SKIP to QUESTION 42 Refused [9] SKIP to QUESTION 42

[NHSDA- Adapted]

If you had more than one main partner during the past 12 months, we would like you to think of the main partner you had last sex with.

9. When was the first time you had sex with your main partner?

____ / ____ (month/year)

10. When was the last time you had sex with your main partner?

____ / ____ (month/year)

11. Is this person a man or a woman?

Man [1] Woman [2] Refused [9]

**If partner is male (Question 11= 1), then SKIP to QUESTION 16

12. The last time you had sex with your main partner, did you have vaginal sex, where your penis entered your partner's vagina?

Yes [1] No [2] SKIP to QUESTION 14 Refused [9] SKIP to QUESTION 14

13. Was a condom used?

Yes [1] No [2] Refused [9]

14. The last time you had sex with your main partner, did you have oral sex, where your mouth touched your partner's vagina?

Yes [1] No [2] SKIP to QUESTION 16 Refused [9] SKIP to QUESTION 16

15. Was a barrier (dental dam, plastic wrap, etc) used?

Yes [1] No [2] Refused [9]

16. The last time you had sex with your main partner, did you have oral sex, where your penis entered your partner's mouth?

Yes [1] No [2] SKIP to QUESTION 18 Refused [9] SKIP to QUESTION 18

17. Was a condom used?

Yes [1] No [2] Refused [9]

18. The last time you had sex with your main partner, did you have anal sex, where your penis entered your partner's anus (butt)?

Yes [1] No [2] SKIP to QUESTION 20 Refused [9] SKIP to QUESTION 20

19. Was a condom used?

Yes [1] No [2] Refused [9]

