9.5 Follow-up

All follow-up assessments will be performed over the phone. Follow-up assessments will occur at 30, 60, and 90 days post enrollment.

Follow-up assessments will include:

- 1) Attitudes toward Pre-Exposure Prophylaxis Scale (APS) (Appendix 3)
- 2) Section 4 of ICAP "Screening for Substantial Risk of HIV" (Appendix 5)
- 3) Satisfaction questionnaire and qualitative assessment and visit specific satisfaction instrument (VSQ-9) (Appendix 6)
- 4) Adherence information measured by (1) self-report. Self-report will be assessed with the single measure Guidelines Regimen Information Program (GRIP) guide and questions on last dose and number of missed doses since prior follow-up. (Appendix 7)
- 5) CDC Sexual Behavior Questions (CSBQ) (Appendix 4)
- 6) STAR*D PRISE (Side-effect assessment)

Assessment of engagement in PrEP care at 30, 60, and 90 days post enrollment will be verified by direct contact with the treatment provider/program provided or by EMR review if the patient is linked within the Mount Sinai Health System. If the patient is receiving their PrEP care outside of the Mount Sinai Health System, a signed release authorization form will be sent.

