11.0 DATA MANAGEMENT AND STATISTICAL ANALYSES

11.1 Statistical Analysis

11.1.1 General approach

Nominal and ordinal categorical variables will be summarized as frequencies and percentages. Continuous variables will be summarized with the following descriptive statistics: N, mean, standard deviation, median, minimum, maximum, interquartile range, and range.

No imputation of missing data will be performed for any of the analysis given the pilot nature of the study and small sample size.

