11.1.2 Analysis of Primary and Secondary Outcomes

Analysis will be on an intention-to-treat basis. In statistical analyses, participants will be included to the date of their last active follow-up visit. Comparisons between control and experimental (iPrEP) arms. To assess the success of randomization, a summary of the baseline variables by treatment group will be tabulated and univariate comparisons performed. The primary outcome, retention in care and PrEP usage, will be compared with proportions and Fisher's exact derived confidence intervals. Secondary outcomes: Secondary analysis will focus on determining how retention in care, risk behavior, adherence or STI diagnosis differ between the groups at any of the follow-up time points. PrEP adherence based on pill counts will be calculated by dividing the number of pills taken by the number of pills prescribed. Adherence will be calculated by study month for each participant. Group adherence comparisons will be compared using Wilcoxon rank sum test. Retention in care, STI diagnosis and risk behavior at each time point will be analyzed for each study visit. Retention in care and STI diagnosis will be treated as dichotomous variables for analysis. Measures of risk behavior will include consistency of condom use and number of sexual partners since prior study visit. Condom use will be treated as an ordinal variable and number of sexual partners as a continuous variable for analysis.

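### Risk behavior is analysed since the prior visit, but the follow-up forms look back 12 or 6 months, so a participant with no sex in the interval is scored on older behavior, and no rule covers the few who skip out

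*Combined protocol and SAP*

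**What the plan says.** Section 11.1.2 defines the outcome: "Measures of risk behavior will include consistency of condom use and number of sexual partners since prior study visit". It adds the scale: "Condom use will be treated as an ordinal variable and number of sexual partners as a continuous variable for analysis". It lists no levels for the ordinal variable and does not mention participants who had no sex in the interval. The same section states that analysis is by intention to treat.

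Section 9.5 sets the timing, "Follow-up assessments will occur at 30, 60, and 90 days post enrollment", and lists both the CSBQ and ICAP Section 4 among the follow-up assessments. Section 10.4.14 names only enrollment for the CSBQ.

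Appendix 4 prints three CSBQ versions (first tier, alternate first tier, second tier). Each opens by asking about sex in the past 12 months, with the routing "Yes [1] No [2] SKIP to END Refused [9] SKIP to END", and then asks for the number of partners over the same 12 months. The first-tier condom item is yes or no about one act: "thinking back about the last time you had sex, did you or your partner use a condom". The other two versions also ask about the last act, by partner type or by type of sex. The plan does not say which version is used.

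The ICAP prompts in Appendix 5 ask about partner number and consistent condom use over 6 months.

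On missing values, Section 11.1.1 says: "No imputation of missing data will be performed for any of the analysis given the pilot nature of the study and small sample size". Nothing separates an item skipped because it does not apply from one that is truly missing.

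**The concern.** The analysis needs behavior over roughly 30 days, and neither follow-up form asks for it. The mismatch touches everyone, but it is sharpest for a participant who has had no sex since the last call. The correct partner count for that person is 0, and condom consistency is undefined. The forms return something else: a 12-month count and an answer about an act that may predate randomization.

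Having sex after randomization is itself part of risk behavior. If abstinence is recorded as earlier activity, a reduction in risk cannot show. If abstinent people were instead left out, the comparison would be restricted by a post-randomization event and would no longer be between the randomized groups. Aim 1b also wants means and standard deviations to plan a definitive trial, and a partner mean that has lost its zeros is too high for that purpose.

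**Working it through.** The plan states no figure for this outcome, so there is none to reproduce. The check sets recall windows against visits and follows the routing.

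**Inputs.** Visits at days 30, 60 and 90 (Section 9.5). CSBQ window 12 months, taken as 365 days (Appendix 4). ICAP window 6 months, taken as 183 days (Appendix 5). Behavioral eligibility on the ICAP screen (Section 9.1).

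**Step 1: how much of each window precedes enrollment.** Days before enrollment = window − visit day.

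| Visit | CSBQ, 365 days | ICAP, 183 days |
|---|---|---|
| Day 30 | 335 (92%) | 153 (84%) |
| Day 60 | 305 (84%) | 123 (67%) |
| Day 90 | 275 (75%) | 93 (51%) |

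The interval being analysed is 30/365 = 8% of the CSBQ window and 30/183 = 16% of the ICAP window.

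**Step 2: who can answer No to item 1.** Someone who entered on sexual risk had sex at most about 183 days before enrollment. At day 90 that act is at most 183 + 90 = 273 days old, which is less than 365. A truthful answer is Yes at every follow-up. The only ICAP route that does not imply recent sex is category 2, shared injection equipment. Its size is not given, though Section 9.1 looks for injection-related complaints and Section 16.0 prioritizes overdose or withdrawal, so it need not be empty.

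**Step 3: what is recorded when there was no sex in the interval.**
- *Entered on sexual risk.* The true count is 0 and the recorded count is at least 1. If a share q of an arm is abstinent, these people alone raise the arm mean by at least q × 1: for an assumed q of 10% to 40%, by at least 0.1 to 0.4 partners. The condom answer describes an earlier act. Someone abstinent since enrollment would report the same pre-randomization act at all three calls.
- *Entered only through shared equipment, no sex in 12 months.* No is recorded as code 2 and the later items are blank. Zero partners follows from the answer, but no rule says to derive it. Condom use is undefined.

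**Step 4: what happens if only the window is corrected.** With item 1 re-anchored to the interval and nothing else changed, every abstinent participant would answer No and go to END. As an illustration, assume 2 partners on average among the active and 40 per arm. With q from 10% to 40%, the true mean is (1 − q) × 2 = 1.8 to 1.2. If the blanks were left out, it would read 2.0, on 36 to 24 participants. If the arms differed only in q, 10% against 30%, the true means would be 1.8 and 1.4, a difference of 0.4, and the analysed difference would be 0.

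**The case against.** The strongest reply is that the skip routing hardly matters on the printed form. Step 2 bears this out: most participants cannot reach END through No. For those who can, No (code 2) is stored apart from Refused (code 9), so 0 partners can be derived from a known answer without breaching the no-imputation rule. No section says such people are excluded, and Section 11.1.2 declares intention to treat. All of this stands.

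It can also be said that other items fill the gap. ICAP Section 4 is repeated at each call and asks about consistency, which is closer to Section 11.1.2 than the CSBQ last-act items. The second-tier CSBQ records the month and year of last sex. These help only in part. Half or more of the ICAP window precedes enrollment at every visit. The tier is unspecified, a month is too coarse for a 30-day interval, and the women's questions on non-main partners word the date items as being about the main partner. Even a usable date would show that an interval was abstinent, without giving the partner count or condom consistency for those who were active.

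Finally, risk behavior is one of several exploratory outcomes in a pilot that declares itself underpowered. That limits the weight of the point, not its correctness.

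**Conclusion.** The point holds as a mismatch between the analysed interval and the recall periods, together with the lack of a scoring rule for no sex. On the printed forms, a participant with no sex since the prior visit is usually scored on older behavior, and the analyst cannot repair this later because the interval data are not otherwise collected.

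A reader might infer more: that the routing leaves the lowest-risk participants without a valid value on either measure, so that they drop out of both comparisons. The documents do not support this. The 12-month window keeps most of them on the Yes branch, a No implies 0 partners, and exclusion would be read into silence. Restriction to the sexually active is a risk of a partial correction (Step 4), not a feature of the present text.

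The size of the effect is unknown. The documents give no abstinence rate, so the figures in Step 4 and the range for q are assumptions. The recall arithmetic assumes truthful answers and that the CSBQ is given at follow-up, as Section 9.5 says. The impact is confined to a secondary outcome and to planning figures for the later trial.

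**What to change.** 1. On the follow-up CSBQ, ask item 1, the partner count and condom use for the period since the prior visit. The enrollment form can keep its 12-month wording, since Section 11.1.2 compares arms at follow-up and does not plan change from baseline.
2. State in Section 11.1.2 that No means 0 partners, as a known answer and not an imputed one, and that Refused stays missing. Compare partner number in everyone who completed the call.
3. For condom use, prespecify one of two options: an ordinal variable for overall exposure with a level for no sex, compared in everyone who completed the call; or consistency among the sexually active, reported as description only. The first changes the construct from condom consistency to overall exposure, so the choice should be stated. Either needs a condom item that can yield ordered levels, which one yes-or-no item on the last act cannot.
4. Reconcile Sections 9.5 and 10.4.14 on whether the CSBQ is given at follow-up, and name the version used.

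The cost is a few reworded items, one scoring rule and two or three sentences in the plan. Steps 1 and 2 must go together, because re-anchoring without the rule invites the restriction shown in Step 4 of the working. The forms must change before the calls are made.

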**If main partner is female (Question 11 = 2) , then SKIP to QUESTION 24 **

The last time you had sex with your main partner did you have anal sex where your partner's penis entered anus (butt)?

Yes [1] No [2] SKIP to QUESTION 22 Refused [9] SKIP to QUESTION 22

Was a condom used?

Yes [1] No [2] Refused [9]

22. The last time you had sex with your main partner, did you have oral sex, where your partner's penis entered your mouth?

Yes [1] No [2] SKIP to QUESTION 24 Refused [9] SKIP to QUESTION 24

23. Was a condom used?

Yes [1] No [2] Refused [9]

24. The last time you had sex with your main partner, were you under the influence of alcohol? Yes [1] No [2] Refused [9] [modified from NHSLS]

25. The last time you had sex with your main partner, had you been using drugs to get high before or during sex?

Yes [1] SKIP to QUESTION 42 No [2] SKIP to QUESTION 42 Refused [9] SKIP to QUESTION 42 [modified from NHSLS]

[FEMALE RESPONDENTS]

The next questions are about sex with a main partner.

26. In the past 12 months have you had sex with someone who you consider to be your main sex partner, that is a partner who you feel committed to above anyone else?

Yes [1] No [2] SKIP to QUESTION 60 Refused [9] SKIP to QUESTION 60 [NHSDA- Adapted]

27. When was the first time you had sex with your main partner?

____/_____(month/year)

28. When was the last time you had sex with your main partner?

____/_____(month/year)

29. Is this person a man or a woman?

Man [1] Woman [2] Refused [9]

If partner is female (Question 29 = 2), then SKIP to QUESTION 36

30. The last time you had sex with your main partner, did you have vaginal sex, where your partner's penis entered your vagina?

Yes [1] No [2] SKIP to QUESTION 32 Refused [9] SKIP to QUESTION 32

31. Was a condom used?

Yes [1] No [2] Refused [9]

32. The last time you had sex with your main partner, did you have oral sex, where your partner's penis entered your mouth?

Yes [1] No [2] SKIP to QUESTION 34 Refused [9] SKIP to QUESTION 34

33. Was a condom used?

Yes [1] No [2] Refused [9]

34. The last time you had sex with your main partner, did you have anal sex, where your partner's penis entered your anus (butt)?

Yes [1] No [2] SKIP to QUESTION 36 Refused [9] SKIP to QUESTION 36

35. Was a condom used?

1] No [2] Refused [9]

Effective Date: 4/20/2021

End Date: 3/18/2022

1] No [2] SKIP to QUESTION 38 Refused [9] SKIP to QUESTION 38

37. Was a barrier (dental dam, plastic wrap, etc) used?

Yes [1] No [2] Refused [9]

If partner is male (Question 29 = 1), then SKIP to QUESTION 40

38. The last time you had sex with your main partner, did you have oral sex, where your mouth touched your partner's vagina?

Yes [1] No [2] SKIP to QUESTION 60 Refused [9] SKIP to QUESTION 60

39. Was a barrier (dental dam, plastic wrap, etc) used?

Yes [1] No [2] Refused [9]

40. The last time you had sex with your main partner, were you under the influence of alcohol? Yes [1] No [2] Refused [9] [modified from N HLSLS]

41. The last time you had sex with your main partner, had you been using drugs to get high before or during sex?

Yes [1] SKIP to QUESTION 60 No [2] SKIP to QUESTION 60 Refused [9] SKIP to QUESTION 60 [modified from N HLSLS]

[MALE RESPONDENTS ONLY]

The next series of questions are about sex with someone who is/was not your main partner.

42. In the past 12 months, have you had sex with someone who is not your main partner or whom you did not consider to be your main partner at the time?

Yes [1] No [2] SKIP to END Refused [9] SKIP to END

For the next series of questions, think back to the last time you had sex with someone who is/was not your main partner.

43. When was the first time you had sex with this partner?

____ / ____ (month/year)

44. When was the last time you had sex with this partner?

____ / ____ (month/year)

45. Is this person a man or a woman?

Man [1] Woman [2] Refused [9]

If partner is male (Question 45 = 1), then SKIP to QUESTION 50

46. The last time you had sex with this partner, did you have vaginal sex, where your penis entered your partner's vagina?

Yes [1] No [2] SKIP to QUESTION 48 Refused [9] SKIP to QUESTION 48

47. Was a condom used?

Yes [1] No [2] Refused [9]

48. The last time you had sex with this partner, did you have oral sex, where your mouth touched your partner's vagina?

Yes [1] No [2] SKIP to QUESTION 50 Refused [9] SKIP to QUESTION 50

'as a barrier (dental dam, plastic wrap, etc) used?

Yes [1] No [2] Refused [9]

The last time you had sex with this partner, did you have oral sex, where your penis entered your partner's vagina? Yes [1] No [2] SKIP to QUESTION 52 Refused [9] SKIP to QUESTION 52

51. Was a condom used?

Yes [1] No [2] Refused [9]

52. The last time you had sex with this partner, did you have anal sex, where your penis entered your partner's anus (butt)?

Yes [1] No [2] SKIP to QUESTION 54 Refused [9] SKIP to QUESTION 54

53. Was a condom used?

Yes [1] No [2] Refused [9]

If partner is female (Question 45 = 2), then SKIP to QUESTION 58.

54. The last time you had sex with this partner did you have anal sex where your partner's penis entered your anus (butt)?

Yes [1] No [2] SKIP to QUESTION 56 Refused [9] SKIP to QUESTION 56

55. Was a condom used?

Yes [1] No [2] Refused [9]

56. The last time you had sex with this partner, did you have oral sex, where your partner's penis entered your mouth?

Yes [1] No [2] SKIP to END Refused [9] SKIP to END

57. Was a condom used?

Yes [1] SKIP to END No [2] SKIP to END Refused [9] SKIP to END

58. The last time you had sex with this partner, were you under the influence of alcohol? Yes [1] No [2]

Refused [9] [modified from NHSLS]

59. The last time you had sex with this partner, had you been using drugs to get high before or during sex?

Yes [1] SKIP to END No [2] SKIP to END Refused [9] SKIP to END

[modified from NHSLS]

[FEMALE RESPONDENTS]

The next series of questions are about sex with someone who is/was not your main partner.

60. In the past 12 months, have you had sex with someone who is not your main partner or whom you did not consider to be your main partner at the time?

Yes [1] No [2] SKIP to END Refused [9] SKIP to END

61. When was the first time you had sex with your main partner?

____/____ (month/year)

62. When was the last time you had sex with your main partner?

____/____ (month/year)

63. Is this person a man or a woman?

Man [1] Woman [2] Refused [9]

If partner is female (Question 63 = 2), then SKIP to QUESTION 70.

64. The last time you had sex with this partner, did you have vaginal sex, where your partner's penis entered your vagina?

Yes [1] No [2] SKIP to QUESTION 66 Refused [9] SKIP to QUESTION 66

'as a condom used?

Yes [1] No [2] Refused [9]

66. The last time you had sex with this partner, did you have oral sex, where your partner's penis entered your mouth?

Yes [1] No [2] SKIP to QUESTION 68 Refused [9] SKIP to QUESTION 68

67. Was a condom used?

Yes [1] No [2] Refused [9]

68. The last time you had sex with this partner, did you have anal sex, where your partner's penis entered your anus (butt)?

Yes [1] No [2] SKIP to QUESTION 70 Refused [9] SKIP to QUESTION 70

69. Was a condom used?

Yes [1] No [2] Refused [9]

70. The last time you had sex with this partner, did you have oral sex, where your partner's mouth touched your vagina?

Yes [1] No [2] SKIP to QUESTION 72 Refused [9] SKIP to QUESTION 72

71. Was a barrier (dental dam, plastic wrap, etc) used?

Yes [1] No [2] Refused [9]

If partner is male (Question 63 =1), then SKIP to QUESTION 74.

72. The last time you had sex with this partner, did you have oral sex, where your mouth touched your partner's vagina?

Yes [1] No [2] SKIP to QUESTION 74 Refused [9] SKIP to QUESTION 74

73. Was a barrier (dental dam, plastic wrap, etc) used?

Yes [1] No [2] Refused [9]

74. The last time you had sex with this partner, were you under the influence of alcohol?

Yes [1] No [2] Refused [9]

[modified from N HLSLS]

75. The last time you had sex with this partner, had you been using drugs to get high before or during sex?

Yes [1] No [2] Refused [9]

[modified from N HLSLS]

